1.0 PROTOCOL SUMMARY AND/OR SCHEMA

ASSESSd

- Eligibility
 - Organ-confined prostate cancer
 - Intermediate risk patients
 - PSA 10-20 ng/ml, or Gleason score = 7 or clinical stage T2b/T2c
- Obtain Informed Consent
- Register Patient

INTERVENTION

- Prostate brachytherapy low dose rate (Pd-103)

THEN after 4 weeks

- Hypofractionated image-guided external beam radiation therapy to prostate and seminal vesicles - (25 Gy in 5 fractions)

POST TREATMENT EVALUATIONS (months 1, 3, 6, then every 6 months for 36 months)

- International Prostate Symptom Score (IPSS)
- International Index of Erectile Function (IIEF)
- Toxicity based on NCI CTCAE (v4.0)
- EPIC
- DRE
- PSA
- Prostate biopsy once at 24-36 months

This study will enroll participants with localized, intermediate risk prostate cancer (T2b/c or Gleason 7 or PSA 10-20 ng/mL). Patients enrolled in the study will undergo low dose rate (LDR) prostate brachytherapy using Pd-103 followed approximately 4 weeks later with hypofractionated image-guided external beam radiation therapy (25Gy in 5 fractions; 5Gy x 5 fractions every other day) to the prostate and seminal vesicles. Both brachytherapy as well as external beam will be performed according to our current standards of practice using the same equipment, techniques, and treatment planning procedures.

Patients will be followed post-treatment at 1, 3, 6 (+/- 4 weeks) and every 6 months (+/- 4 weeks) thereafter until 36 months. During the post-treatment followup, patients will be evaluated for urinary, bowel/rectal and sexual toxicity. Toxicity will be assessed according to CTCAE v4.0, IPSS, IIEF and EPIC validated instruments. Baseline measures of these domains will be obtained prior to treatment at the time of enrollment. Serum PSA levels will be drawn on the same schedule as clinical followup. Post-treatment prostate biopsies will be obtained once between 24-36 months post-treatment to evaluate pathologic response to therapy.

The total number of participants enrolled will be 45 to be accrued in approximately 3 years.

2.1 OBJECTIVES AND SCIENTIFIC AIMS

Primary Objective:

- Evaluate late urinary toxicity as assessed by CTCAE v4.0 at approximately 12 months of hypofractionated radiation therapy in combination with brachytherapy for the treatment of intermediate risk prostate cancer.

Secondary Objectives:

- Assess IPSS changes
- Evaluate late rectal and erectile toxicity
- Evaluate PSA relapse-free survival
- Evaluate local control based on post-treatment prostate biopsy at 24-36 months

3.0 BACKGROUND AND RATIONALE

The goal of radiation therapy for prostate cancer is to deliver high doses to the target (i.e. prostate +/- seminal vesicles) while reducing dose to normal surrounding tissue. Brachytherapy is a particularly effective way to achieve this goal as radiation sources are placed directly into target tissue with very rapid dose fall off. Dose escalation strategies include a combination of brachytherapy and conformal external beam radiation therapy and outcomes using this treatment appear to compare favorably to external beam radiation therapy approaches.^{1, 2} Typical external beam radiation therapy courses in this setting are 4-5 weeks of daily radiotherapy using fraction sizes of 1.8-2 Gy. An emerging body of literature suggests that hypofractionated schedules may

be superior to conventional fractionation schemes in terms of both tumor control and toxicity for prostate cancer. The use of hypofractionated radiation therapy combined with brachytherapy has not been investigated; however in addition to a potential radiobiologic benefit, this approach may also be more convenient for patients and reduce the burden of therapy as well.

Radiobiology of Prostate Cancer

To maximize the therapeutic ratio, a fractionation schedule of radiotherapy should optimize the dose per fraction with respect to the sensitivity of the tumor relative to normal tissues. In most cancers, adjacent late responding tissues are more sensitive to increased fraction dose than tumors. For this reason most radiation regimens utilize small daily fraction sizes (1.8-2Gy) to maximize the therapeutic ratio. Radiobiologic research however suggests that prostate cancer may not optimally respond to these standard fraction sizes and may benefit from delivery of higher doses per fraction.

The suggestion that prostate cancer may have a unique radiobiology was suggested by Brenner and Hall who observed that biochemical control was similar for 70 Gy given in 1-2Gy fractions and I-125 brachytherapy using a prescription dose of 144Gy.³ Subsequent studies by others have demonstrated that the α/β (ratio of intrinsic radiosensitivity to repair capacity) for prostate cancer ranges between 1.5-1.85.^{4, 5} This low α/β ratio predicts a greater capacity for repair between fractions, with an accompanying greater relative sparing with smaller fraction sizes. Therefore, a higher dose per fraction may be particularly beneficial for prostate cancer cell death.

BED calculations for current study:

Using the BED equation:

$$nd(1+d/\alpha/\beta)$$

where:

n=number of fractions

d=dose per fraction

α/β = 1.5, 3, and 10

	45Gy/1.8Gy	25Gy/5Gy
BED ($\alpha/\beta=1.5$)	99	108
BED ($\alpha/\beta=3$)	72	68
BED ($\alpha/\beta=10$)	53	37.5

Similar BEDs are expected to be isoeffective or have the same biologic effect. An α/β of 10 is assumed for early-responding tissues and 3 for late-responding tissues. An α/β of 1.5 is used for prostate cancer).

Safety of Hypofractionation for Prostate Cancer

Hypofractionated radiotherapy for prostate cancer has been studied since the 1960s.⁶ Early experience using 36Gy delivered in 6Gy fractions reported minimal acute and long term toxicity with this approach. This early experience utilized relatively crude planning techniques as compared with more modern approaches, however despite this; hypofractionated therapy

appeared to be safe. Since this early experience, many subsequent studies have demonstrated that toxicity of hypofractionated regimens using brachytherapy or external beam radiation appear at least comparable if not more favorable to conventionally fractionated regimens.^{7, 8, 9, 10} Katz et al reported toxicity outcomes in patients receiving up to 36.25Gy in 7.25Gy fractions at a median followup of 60 months. In this group, acute grade 3-4 toxicity was noted in 0% and late grade 3 urinary toxicity in 2% of patients. In a study by Bhattacharjee et al, 228 predominantly low- and intermediate-risk prostate cancer patients were treated with 35-36.25Gy in 5 fractions.¹¹ With a minimum followup of 24 months, EPIC urinary and bowel bother scores were transiently elevated at 1 month following treatment and declined to near-baseline by 2 years. Moderate to severe urinary or bowel bother was noted in 8% and 2.5% of patients respectively. Several studies are ongoing to determine the optimal duration and dose using hypofractionated regimens. Our group is currently conducting a dose escalation hypofractionated approach (IRB protocol #09-035), which will help establish the optimal dose delivered in a 5 fraction regimen.

Brachytherapy combined with external beam radiation therapy for prostate cancer

LDR brachytherapy combined with conventional external beam radiotherapy for patients with intermediate risk prostate cancer addresses not only a need for dose escalation but also addresses concerns of dose coverage of extracapsular disease extension and is an accepted standard of care approach for intermediate risk disease (www.nccn.org). Long term outcomes using either LDR brachytherapy have been reported.^{12, 13, 15} We recently reported 7-year PSA relapse-free survival of 92% for patients with intermediate risk prostate cancer treated with prostate brachytherapy combined with 50.4Gy of external beam radiotherapy.¹⁴ With regards to toxicity, acute and late grade 3 or higher GU toxicity was noted in 2.3% and 3.1% respectively. Grade 2 late GU and GI toxicity were 21% and 4% respectively.

Although hypofractionated regimens for the definitive treatment of prostate cancer are considered part of a standard approach, the integration of a hypofractionated approach combined with brachytherapy has not yet been studied. To date, two ongoing studies are examining this in a Phase I setting (www.clinicaltrials.gov). The purpose of this study is to establish the toxicity associated with brachytherapy combined with hypofractionated radiation therapy.

4.1 OVERVIEW OF STUDY DESIGN/INTERVENTION

4.2 Design

Patients enrolled in this study will undergo LDR prostate brachytherapy followed approximately 4 weeks later with hypofractionated, image-guided intensity modulated radiation therapy to a dose of 25Gy in 5 fractions of 5Gy delivered every other day. Radiobiologically, as indicated in the BED calculations in Section 3, the dose of hypofractionated radiotherapy is expected to have less acute toxicity and equivalent late toxicity as standard fractionated treatment. Both brachytherapy and hypofractionated external beam radiation therapy will be delivered using the same equipment, techniques and treatment planning procedures as currently practiced at MSKCC.

Patients will be followed post-treatment at 1, 3, 6 (+/- 4 weeks) and every 6 months (+/- 4 weeks) thereafter until 36 months. During the post-treatment followup, patients will be evaluated for urinary, bowel/rectal, and sexual toxicity. Baseline measures of these domains will be obtained prior to treatment. The primary endpoint will be urinary toxicity as assessed by CTCAE v4.0 at 12 months. Bowel and sexual function will also be assessed at followup as

secondary endpoints. Serum PSA levels will be drawn on the same schedule as clinical followup. Post-treatment prostate biopsies will be obtained once at 24-36 months post-treatment to evaluate pathologic response to therapy.

4.3 Intervention

Patients enrolled in this study will undergo LDR prostate brachytherapy followed approximately 4 weeks later with hypofractionated, image-guided intensity modulated radiation therapy to a dose of 25Gy in 5 fractions of 5Gy delivered every other day. Both brachytherapy and hypofractionated external beam radiation therapy will be delivered using the same equipment, techniques and treatment planning procedures as currently practiced at MSKCC.

Patients will undergo a prostate brachytherapy procedure as currently practiced at MSKCC. The prescribed radiation dose will remain our standard prescription dose of 100Gy using Pd-103. The dose constraints for brachytherapy treatment planning will remain the same. For patients with large prostate volumes (>60cc), cytoreductive androgen deprivation will be allowed for a maximum duration of 6 months prior to brachytherapy. For patients with a prostate volume between 50-60ccs, hormone therapy will be at the discretion of the physician.

Approximately 4 weeks following brachytherapy, the patient will undergo hypofractionated image-guided intensity modulated radiation therapy (25Gy in 5 fractions delivered every other day). Dose constraints for treatment planning are presented in Section 9 and were modeled based on our current standard guidelines for hypofractionated therapy and our constraints for standard fractionation external beam radiotherapy post-brachytherapy. Radiation therapy will be delivered every other day, Monday through Friday until 5 treatments are completed. Daily target motion will be monitored and corrected, using fiducial markers implanted at the time of brachytherapy as per the routine standard in our Department for patients who receive external beam radiotherapy.

5.1 THERAPEUTIC/DIAGNOSTIC AGENTS

No investigational devices, new agents, new equipment, nor new radiation techniques will be used in the protocol. The brachytherapy procedure is performed using our current standard procedures, equipment, treatment planning and dosing. A detailed step-by-step account of the procedures for simulation, planning and treatment are detailed in Section 9.0. Radiation will be delivered every other day, Monday through Friday until 5 treatments are completed. Daily target motion will be monitored and corrected using fiducial markers implanted at the time of brachytherapy. All treatment is given on an outpatient basis.

6.1 CRITERIA FOR SUBJECT ELIGIBILITY

6.2 Subject Inclusion Criteria

Intermediate risk prostate cancer patients will be eligible for this study. Intermediate risk grouping will be assessed per NCCN guidelines as:

- Pathologically-proven diagnosis of prostate adenocarcinoma

- PSA 10-20ng/mL or
- Gleason =7 or
- Clinical stage T2b/c

Additionally, patients will be required to meet the following criteria

- Age ≥ 18
- KPS ≥ 70
- Prostate volume $\leq 60\text{cc}$ (cytoreductive androgen deprivation therapy prior to brachytherapy of ≤ 6 months duration will be allowed to achieve this goal). For patients with a prostate volume between 50-60ccs, hormone therapy will be at the discretion of the physician.
- International Prostate Symptom Score ≤ 15

6.3 Subject Exclusion Criteria

- Prior prostate surgery (including TURP)
- Prior history of chronic prostatitis or urethral stricture
- Inflammatory bowel disease
- Prior history of pelvic radiotherapy
- Unable to give informed consent
- Metastatic disease.

7.0 RECRUITMENT PLAN

Potential research subjects will be identified by a member of the patient's treatment team, the protocol investigator, or research team at Memorial Sloan-Kettering Cancer Center (MSKCC). If the investigator is a member of the treatment team, s/he will screen their patient's medical records for suitable research study participants and discuss the study and their potential for enrolling in the research study. Potential subjects contacted by their treating physician will be referred to the investigator/research staff of the study.

We expect that the study population will be fully representative of the range of patients seen at MSKCC without exclusion to age (≥ 18 years) or ethnic background. Given the limited patient number to be entered onto the study, no specific outreach efforts are planned. It is expected that approximately 5 potentially eligible patients will be seen weekly in consultation amongst the 4 consenting physicians. If stopping rules are not met, it is anticipated that this protocol will take approximately 3 years to accrue.

During the initial conversation between the investigator/research staff and the patient, the patient may be asked to provide certain health information that is necessary to the recruitment and enrollment process. The investigator/research staff may also review portions of their medical records at MSKCC in order to further assess eligibility. They will use the information provided by the patient and/or medical record to confirm that the patient is eligible and to contact the patient regarding study enrollment. If the patient turns out to be ineligible for the research study, the research staff will destroy all information collected on the patient during the initial conversation and medical records review, except for any information that must be maintained for screening log purposes.

In most cases, the initial contact with the prospective subject will be conducted either by the treatment team, investigator or the research staff working in consultation with the treatment team. The recruitment process outlined presents no more than minimal risk to the privacy of

the patients who are screened and minimal PHI will be maintained as part of a screening log. For these reasons, we seek a (partial) limited waiver of authorization for the purposes of (1) reviewing medical records to identify potential research subjects and obtain information relevant to the enrollment process; (2) conversing with patients regarding possible enrollment; (3) handling of PHI contained within those records and provided by the potential subjects; and (4) maintaining information in a screening log of patients approached (if applicable).

8.1 PRETREATMENT EVALUATION

- MSKCC prostate biopsy or pathology review of prostate biopsy material
- Full history and physical examination *within 6 weeks of enrollment*
- *Digital Rectal Exam (DRE) within 3 months of enrollment*
- Pretreatment PSA *within 6 weeks of enrollment*
- Pelvic MRI or CT (MRI preferred) *within 6 months of enrollment*
- Bone scan if there is suspicion of bone metastases *within 6 months of enrollment*
- Baseline IPSS, IIEF, and EPIC survey *within 6 weeks of enrollment (repeated within 4 weeks prior to brachytherapy for patients undergoing cytoreductive hormone therapy)*

9.1 TREATMENT/INTERVENTION PLAN

Brachytherapy Procedure (all steps as per current departmental procedure):

- Patients undergo general anesthesia for outpatient interstitial brachytherapy
- Transrectal guidance of implanted fiducial markers into the prostate
- Transrectal ultrasound utilized to guide needles/seeds into the prostate gland
 - LDR procedure:
 - Pd103 radioactive seeds inserted according to intraoperative plan using MICK applicator and ultrasound/fluoroscopic guidance.
 - Prescription dose= 100Gy to the prostate
 - Postoperative CT-based dosimetry following procedure
- Following completion of brachytherapy treatment, Foley catheter removal and voiding trial
- Discharge home

Hypofractionated Radiation Therapy:

Simulation (all steps as per current departmental procedure):

- Approximately 2 weeks following interstitial brachytherapy, a simulation for hypofractionated external beam radiation therapy will take place.
- A bowel preparation will be performed the night before simulation.
- Patients will be instructed to maintain a full bladder during simulation and treatment.
- Patients will be supine and positioned in a thermoplastic mold.
- A Foley and rectal catheter will be placed for simulation only.
- CT images will be obtained as per existing department protocols and used for treatment planning purposes.

Treatment Planning:

- The gross tumor volume (GTV) will be defined as the prostate gland.
- The clinical tumor volume (CTV) will be defined as the prostate and seminal vesicles.

- The planning target volume (PTV) will be defined as a non-uniform expansion around the CTV: 0.5cm in all directions except posteriorly at the rectal interface which will be 0.3cm.
- Normal tissues to be contoured include:
 - Bladder wall (inner and outer)
 - Rectal wall (inner and outer)
 - Urethra
 - Bilateral femoral heads/neck
 - Large bowel
 - Small bowel
- The following dose constraints will be used for treatment planning:

PTV D95% [Dose to 95% volume]		90%
Rectal wall max	106% of Rx	2650 cGy
Rectal wall D1cc [Dose to 1cc]	103% of Rx	2575 cGy
Rectal wall mean dose		1550 cGy
Urethra max	100% of Rx	2500 cGy
Urethra D1cc [Dose to 1cc]	90% of Rx	2250 cGy
Bladder wall max	106% of Rx	2650 cGy
Bladder wall D5cc [Dose to 5cc]	103% of Rx	2575 cGy
Bladder wall mean dose		1650 cGy
Small/Large Bowel max		2500/2650 cGy
Femur max		2000 cGy

Treatment delivery:

- Patients will be treated every other day (as per standard hypofractionated treatment) Monday- Friday
- Patient set up will be according to simulation parameters (immobilization, full bladder)
- Daily pretreatment in-room imaging will localize target as per department routine
- Any necessary translational shifts will be made and approved prior to treatment.
- Treatment will be delivered as per routine.

10.1 EVALUATION DURING TREATMENT/INTERVENTION

Patients who cannot meet the necessary dosimetric constraints will not be eligible for participation in the study and will be withdrawn from study, since they will already be enrolled at this time

- There will be at least one status check visit during the course of hypofractionated external beam radiotherapy.
- Participants will have clinic follow-up visits at 1, 3, and 6 months (+/- 4wks) posttreatment.
- Then at 6 month intervals (+/- 4wks) post treatment.
- Follow-up scheduling is based on the last day of hypofractionated treatment.
- At each followup visit, patients will undergo standard DRE and serum PSA. Patients will also be asked to complete sexual quality of life questionnaires (EPIC), and urinary and rectal quality of life questionnaires (IPSS and IIEF), which will be captured per standard of care and be assessed for toxicity using CTCAE 4.0. If patient is unable to come in for a followup appointment, a telephone followup will suffice and the PSA and DRE will be deferred. IPSS, IIEF, and EPIC questionnaires can be completed over the phone or sent to patients via mail, fax, or electronic mail by the physician or the physician's office assistant if the patient is unable to come in for a follow-up appointment. If the patient cannot be reached by phone or prefer to complete the questionnaires personally, the questionnaires will be sent via mail, fax or electronic mail. The questionnaires sent directly to patients must be blank forms with no patient identifiers, only study ID numbers. If questionnaires are sent via mail, the patient must be provided with a pre-filled business envelop that will allow patients to return it with no expense. Patients must also have the option of returning questionnaires by electronic mail or fax. If a patient is unable to come in for a follow-up appointment or complete the questionnaires over the phone, the method by which questionnaires are sent to patients and the method by which questionnaires are returned will be determined based on the patient's preference or if they are unable to be contacted by phone, the contact information on file for the patient as some patients may not have access to a phone, fax or electronic mail. A repeat prostate biopsy will be completed between months 24 and 36 for pathologic response assessment. This is a standard assessment tool.

After 36 months, patients will be encouraged and have the option of continued followup through our Prostate Survivorship Clinic for as long as feasible. Continued quality of life (IPSS, IIEF) and disease (PSA, DRE) assessment will be as per standard practice in the Prostate Survivorship Clinic.

	Prior to brachy therapy start unless otherwise indicated	During RT	Month 1, 3, and 6 (+/- 4 weeks)	Month 12-36 (every 6 months +/- 4 weeks)	Once during year 2-3
Pathology review	X				
History and PE	x ¹				
DRE	x ¹		X	X	
PSA	x ¹		X	X	
Prostate biopsy	X (if				X

	applicable)				
Pelvic MRI or CT	X ²				
Bone scan (if deemed necessary)	X ²				
Toxicity assessment (CTCAE 4.0, IPSS, IIEF, EPIC)	X ^{1, 3, 4}		X ⁴	X ⁴	X ⁴
LDR Brachytherapy		X (Once)			
IG-IMRT (every other day)		X			
Status check		X (Once)			
Followup			X	X	X

1 Within 6 weeks of enrollment; comorbidities are captured at baseline

2 Within 6 months of enrollment

3 IPSS, IIEF, and EPIC repeated within 4 weeks prior to brachytherapy for patients undergoing cytoreductive hormone therapy

4 Standard of care IIEF and IPSS Questionnaires will be used

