13.1 CRITERIA FOR REMOVAL FROM STUDY

The study subject will be removed from the study for any of the following reasons after review by the PI:

- 1) A change in patient's medical status unrelated to study treatment results in patient unable to comply with protocol
- 2) Patient is unable to meet dosimetric constraints in Section 9
- 3) Patient is unable to comply with followup schedule.
- 4) Patient request.
- 5) If ineligible for protocol as designated by Section 6, the patient will be removed.

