14.0 BIOSTATISTICS

The primary objective is to assess the toxicity of hypofractionated radiation therapy in combination with brachytherapy for the treatment of intermediate risk prostate cancer. To set up a decision rule we will focus on the CTCAE v 4.0 (see appendix) grade 2 or higher GU toxicity observed at the 1-year follow-up time (+/- 4 weeks). We will enroll 40 evaluable patients, and if 12 or more patients have a CTCAE v4.0 grade 2 or higher toxicity at 1 year, this treatment will be deemed too toxic and the study will be stopped. Otherwise it will be declared safe. This decision rule has the following probabilities of declaring treatment unsafe

True toxicity rate	0.15	0.20	0.25	0.30	0.35	0.40	0.45
Probability of declaring unsafe	1%	8%	28%	56%	79%	92.9%	98.2%

Patients who withdraw, die due to reasons other than toxicity, or fail to provide the 1-year CTCAE v4.0 GU toxicity status will be replaced by new patients. To this end we may need to enroll an additional 4 patients (10%).

For the secondary objectives, all toxicities will be tabulated by type and grade. Post-treatment PSA values will be summarized numerically and graphically. Time to PSA relapse will be analyzed by Kaplan-Meier estimation. The pathologic response rates at 24-36 months will be calculated as sample proportion based on the available patients and confidence intervals will be provided. Erectile function evaluated by IIEF will be summarized by descriptive statistics.

It is expected that it will take approximately 3 years to accrue the total of 45 patients.

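### Men who fail the external-beam dose constraints are withdrawn after their Pd-103 implant: they have no scheduled late-toxicity follow-up, are not reported, and fall outside a safety verdict that is worded without limits

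*Combined protocol and SAP*

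**What the plan says.** - **Order of treatment.** Section 9.1 gives the implant first, then: "Approximately 2 weeks following interstitial brachytherapy, a simulation for hypofractionated external beam radiation therapy will take place". The table introduced by "The following dose constraints will be used for treatment planning" follows under external-beam planning. It has 11 rows: five are urethra or bladder-wall limits, and the other six cover target coverage, rectal wall, bowel and femur.
- **Consequence of missing a constraint.** Section 10.1 says: "Patients who cannot meet the necessary dosimetric constraints will not be eligible for participation in the study and will be withdrawn from study". It acknowledges that they are enrolled by then. Section 13.1 lists the same reason for removal, after review by the principal investigator: "Patient is unable to meet dosimetric constraints in Section 9".
- **Replacement and verdict.** Section 14.0 says: "Patients who withdraw, die due to reasons other than toxicity, or fail to provide the 1-year CTCAE v4.0 GU toxicity status will be replaced". The rule is: "We will enroll 40 evaluable patients, and if 12 or more patients have a CTCAE v4.0 grade 2 or higher toxicity at 1 year", the treatment is judged too toxic. Then: "Otherwise it will be declared safe".
- **Follow-up.** Section 10.1 counts visits from the final day of hypofractionated treatment. Section 17.3 requires SAE reports for 30 days after the last study treatment. After that, only events that are both unexpected and at least possibly related must be reported.

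**The concern.** Eligibility is settled after protocol treatment has begun. A man who fails the constraints carries a 100 Gy implant, yet is treated as if he had never qualified. Two things are at stake.

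First, the trial exists to describe toxicity, and a small group of treated men has no scheduled assessment of late toxicity.

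Second, the verdict refers to the treatment as a whole, while the 40 men behind it are those whose post-implant plan was acceptable. How often an implanted man cannot go on to the second half is part of judging the sequence, and no planned output shows it.

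**Working it through.** **1. What happens to a man who fails the constraints**

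| Step | Source | Result |
|---|---|---|
| Implant given | 9.1 | Half the protocol treatment delivered |
| Simulation about 2 weeks later, then planning | 9.1 | First point at which the table can be checked |
| A constraint is missed | 10.1, 13.1 | Ineligible, withdrawn |
| No 1-year GU grade | 14.0 | Replaced |
| Visits count from last external-beam day | 10.1 | No such date exists for him |
| SAE window of 30 days from last study treatment | 17.3 | Counted from the implant, ends about 2 weeks after simulation |

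Section 14.0 speaks of patients who withdraw, not of patients who are withdrawn, so replacement on that ground is an inference. The missing 1-year status triggers replacement anyway.

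Section 11.1 defines late toxicity as occurring after 90 days, so the 30-day window closes before the late period opens. An expected grade 2 urinary event at 12 months, which is the endpoint itself, is neither on a visit schedule nor normally reportable for him.

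**2. The plan's own figures**

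The probability of declaring unsafe is P(X ≥ 12) with X ~ Binomial(40, p).

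| True rate p | 0.15 | 0.20 | 0.25 | 0.30 | 0.35 | 0.40 | 0.45 |
|---|---|---|---|---|---|---|---|
| Section 14.0 | 1% | 8% | 28% | 56% | 79% | 92.9% | 98.2% |
| Recomputed | 1.2% | 8.75% | 28.5% | 55.9% | 79.5% | 92.9% | 98.2% |

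The table reproduces to within 1 percentage point. It describes men who pass the dose check and have a 1-year grade, not all men implanted.

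**3. Bounds that need no assumption about these men's toxicity**

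With x events in 40 evaluable men and k uncounted implanted men, the rate among all implanted lies between x/(40 + k) and (x + k)/(40 + k). The largest count that still gives a safe verdict is x = 11. The rule's cut-off is 12/40 = 30%.

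| k | Lowest | Highest |
|---|---|---|
| 1 | 11/41 = 26.8% | 12/41 = 29.3% |
| 2 | 11/42 = 26.2% | 13/42 = 31.0% |
| 4 | 11/44 = 25.0% | 15/44 = 34.1% |
| 5 | 11/45 = 24.4% | 16/45 = 35.6% |

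The value k = 4 is the replacement allowance in Section 14.0; k = 5 follows from the stated total, 45 − 40. Both are ceilings, because the allowance also covers voluntary withdrawal, death and missing data. With k = 4 the upper bound reaches 30% only if x is 10 or 11: 14/44 = 31.8% at x = 10, but 13/44 = 29.5% at x = 9.

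**4. Illustration with assumed values**

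Let w be the share of implanted men withdrawn and R the ratio of their toxicity rate to that of retained men. The documents give neither. The retained rate is p_all/(1 − w + wR). For p_all = 0.40, the chance of declaring unsafe is:

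| w | R = 0.5 | R = 1 | R = 1.5 | R = 2 |
|---|---|---|---|---|
| 5% | 94.5% | 92.9% | 91.1% | 89.0% |
| 10% | 95.9% | 92.9% | 89.0% | 84.2% |
| 20% | 97.9% | 92.9% | 84.2% | 72.7% |

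For example, w = 10% and R = 2 give 0.40/1.10 = 0.364, and P(X ≥ 12) = 84.2%. The direction depends wholly on R, and at R = 1 nothing changes.

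**The case against.** The strongest reply concerns what is being estimated. The primary objective is the toxicity of the combination, and Section 4.3 makes the constraints part of how the combination is planned. A man who fails them never receives the protocol external beam and cannot inform its toxicity. He also leaves on a planning result, not on observed toxicity. This stands: excluding him from the 12-of-40 rule is reasonable.

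A reader might go further and infer that the rule removes high-risk men and so biases the toxicity rate downward. The documents do not support that. They give no failure rate and no toxicity for these men, six of the 11 rows do not concern GU organs, and without the external beam these men could have less toxicity rather than more.

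A reader might also infer that they vanish without trace. That is too strong. They are registered, the principal investigator reviews each removal, limited SAE reporting continues, and no text orders assessment to stop. Section 14.0 also tabulates all toxicities without limiting this to the 40. But a table can hold only what is collected, and the visit clock in Section 10.1 gives these men no visit at which a late grade would be recorded.

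**Conclusion.** The point holds as one of follow-up, reporting and scope. By the plan's own rules, men already implanted can be declared ineligible, lose any dated late-toxicity assessment and be replaced, while the verdict is stated without limiting it to men whose plan met Section 9. The decision rule and its operating characteristics are sound for the men they describe.

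The size of any effect is unknown. If all 4 replacement places went to such men, a safe result at its limit (11 of 40) would correspond to 25.0% to 34.1% of all implanted men, on either side of the 30% cut-off. If at most one man failed, or if 9 or fewer of the 40 had events with 4 uncounted, even the worst case stays below 30%. The figures in the illustration rest on assumed values of w and R and are not evidence of bias.

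**What to change.** 1. **Sections 10.1, 13.1 and 14.0.** For this group, replace withdrawal from the study with: not evaluable for the 12-of-40 decision, but followed with CTCAE v4.0 at the scheduled intervals, dated from the implant. The new time origin is essential, because the present one does not exist for these men.
2. **Section 14.0, reporting.** Give the number and percentage of implanted men who failed, by constraint. List their 12-month GU grade descriptively, together with the treatment they later received. Give the lowest and highest possible rate among all implanted men, as in step 3 of the working.
3. **Section 14.0, verdict.** State that a conclusion of safety applies to men whose external-beam plan met the Section 9 constraints.

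The 12-of-40 rule and the dose constraints are left unchanged.

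The cost is protocol wording and CTCAE data entry for what should be a few men. Their data will be confounded by off-protocol treatment and can only be descriptive, and the claim of safety becomes narrower.
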